#### **3.4.1 Exposure**

Exposure (days) is calculated only for subjects in the full analysis set as the total number of days on study drug. Exposure is calculated as the study drug dose last date minus study drug dose first date plus one as reported in the eCRF study treatment log page. If any of the first or last dates are missing or partially missing, then imputed dates will not be used, and study drug exposure is set to missing.

#### **3.4.2 Compliance**

Overall compliance to the IP is calculated only for subjects in the full analysis set.

The percent compliance is defined as the total number of vials consumed divided by the total number of vials that should have been taken where, total number of vials consumed will be calculated as number of kits recorded in the IRT system, number of vials that should have been

taken is calculated as the number of the scheduled dispensation visits (even if not done) before the end of the study.

No replacement of missing data is used. Therefore, if one of the above factors is missing then compliance will be missing.

Compliance is also categorized as:

- < 80%
- $\geq 80\%$  to < 120%
- $\geq 120\%$

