### **Intervention Groups and Duration:**

The screening period starts up to 42 days before the randomization visit and ends on Day -1. Eligible participants will attend 7 visits during the treatment period and 7 additional visits during the safety follow up period. Eligible participants are randomized across four different treatment arms at a 1:1:1:1 ratio for a 12-week treatment period. The planned treatment arms are: AZD8233 **CCI**, AZD8233 **CCI**, AZD8233 **CCI**, and Placebo. Participants will be dosed SC on Days 1, 8, 29, and 57.

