### 6.1 Study Intervention(s) Administered

#### 6.1.1 Investigational Products

Details of the identity of the investigational products are presented in [Table 4](#) and in Handling Instructions D7990C0003, AZD8233 solution for injection. In case of a change of the planned doses (as described in [Section 4.3](#)), the investigational product strength/concentrations may be used for other cohorts than presented in [Table 4](#), in order to minimize injection volume.

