**Table 4 Investigational Products**

|  |  |                          |
|--|--|--------------------------|
| Treatment Administration Guidelines     | Subcutaneous abdominal region injection is the preferred region; avoid a 5 cm radius around umbilicus. Other regions might be used if needed, as decided by the investigator (thigh or buttock). Slow injection of study intervention using gentle pressure (at least 5 seconds duration is recommended) and rotation of injection sites. The anatomical location of each injection site should be documented in the eCRF. |                          |
| Specific device for drug administration | Syringes for injection to be provided by Clinical Team   |                          |
| Use                                     | Experimental   | Placebo to match AZD8233 |
| IMP and NIMP                            | IMP  |                          |
| Sourcing                                | Provided centrally by the Sponsor  |                          |
| Packaging and Labelling                 | Study Intervention will be provided in vials. Each vial will be packed in a separate carton. Each vial and carton will be labelled as required per country requirement   |                          |
| Special Handling Requirements           | Requirements will be provided in a separate document   |                          |
| Availability of IMP                     | Will be shipped when approvals are in place  |                          |

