## 6.3 Measures to Minimise Bias: Randomization and Blinding

All participants will be centrally assigned to randomized study intervention using a RTSM

system. Before the study is initiated, the telephone number and call-in directions and/or the log in information & directions for the RTSM will be provided to each site.

To simplify supply of study drug, randomization will be stratified based on the region in which the site is located. This will achieve greater balance within each region compared to simple randomization. Currently, two regions are planned: Europe and North America.

Study intervention will be dispensed at the study visits summarized in SoA.

The RTSM will provide to the Investigator(s) or pharmacists the kit identification number to be allocated to the participant at the dispensing visit. Routines for this will be described in the RTSM user manual that will be provided to each centre.

The randomisation code should not be broken except in medical emergencies when the appropriate management of the participant requires knowledge of the treatment randomisation. The Investigator documents and reports the action to AstraZeneca, without revealing the treatment given to participant to the AstraZeneca staff. AstraZeneca retains the right to break the code for SAEs that are unexpected and are suspected to be causally related to an investigational product and that potentially require expedited reporting to regulatory authorities. Randomisation codes will not be broken for the planned analyses of data until all decisions on the evaluability of the data from each individual participant have been made and documented.

The RTSM will be programmed with blind-breaking instructions. In case of an emergency, in which the knowledge of the specific blinded study treatment will affect the immediate management of the participant's condition (eg, antidote available), the Investigator has the sole responsibility for determining if unblinding of a participants' intervention assignment is warranted. Participant safety must always be the first consideration in making such a determination. If a participant's intervention assignment is unblinded, the sponsor must be notified within 24 hours after breaking the blind. The Investigator documents and reports the action to AstraZeneca, without revealing the treatment given to participant to the AstraZeneca staff.

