### **3.4 Exposure and treatment compliance**

As per study protocol, subjects start the subcutaneous injections of the study IP at day 1. Then the subjects will be subcutaneously dosed also on Days 8, 29, and 57. Subcutaneous injections should primarily be performed on site. Dosing visits may be undertaken as home visits. If participants are dosed at home, they will receive the study intervention directly from the nurse.

The date, and time if applicable, of dose administered in the clinic and at home, as well as the anatomical location of the injection site, will be recorded in the eCRF.

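### SAP 3.4.2 counts kits recorded in the IRT as vials consumed, so a kit allocated but not injected, or a replacement kit, is reported as a dose taken

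*SAP*

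**What the plan says.** The regimen has four doses: "Participants will be dosed SC on Days 1, 8, 29, and 57" (protocol synopsis). For compliance, SAP 3.4.2 gives a ratio. In the numerator, the "total number of vials consumed will be calculated as number of kits recorded in the IRT system". In the denominator, the quantity due to be "taken is calculated as the number of the scheduled dispensation visits (even if not done) before the end of the study". The population is restricted: "Overall compliance to the IP is calculated only for subjects in the full analysis set", so everyone in the table has received at least one dose. The result is also grouped as below 80%, 80% to below 120%, and 120% or more.

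Protocol 6.3 describes what the allocation system does: "The RTSM will provide to the Investigator(s) or pharmacists the kit identification number to be allocated to the participant at the dispensing visit". Neither document says that the system records whether the injection was given.

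Injections are recorded elsewhere. SAP 3.4 has "The date, and time if applicable, of dose administered in the clinic and at home" entered in the eCRF, along with the injection site. SAP 3.1.1.1 refers to injections, with lot number, in the eCRF treatment log. SAP 3.4.1 takes exposure from that log, but 3.4.2 does not use it for compliance.

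**The concern.** A kit record shows that drug was made available. It does not show that drug was given. Protocol 1.3 and Appendix F 1 make dosing conditional on review of results against the stopping criteria, and Appendix B 4 foresees medication that was prepared but not given. A kit can therefore be on record for a visit without an injection, and a replacement for an unusable vial would add a record without adding a dose. SAP 3.4.2 corrects for neither.

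What is at stake is an accurate description of the doses received in each arm of a trial meant to select a dose. Exposure cannot fill the gap, because it is the last dose date minus the first plus one and so is blind to a missed dose in between. Of these two summaries, only compliance could show such a miss, and its numerator cannot do so reliably.

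**Working it through.** The documents report no compliance value, so there is no stated figure to reproduce. The check applies the SAP formula and compares it with a count of injections.

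**Inputs**
- Scheduled doses and dispensation visits: V = 4, on Days 1, 8, 29 and 57 (protocol synopsis).
- K = kits recorded in the IRT (SAP 3.4.2).
- I = injections in the eCRF treatment log (SAP 3.1.1.1 and 3.4).
- Assumptions: one kit per dose, and the SAP's IRT is the protocol's RTSM.

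**Formulas**
- SAP compliance = 100 × K / V
- Injection-based compliance = 100 × I / V
- Difference = 100 × (K − I) / V, which is 100 × 1/4 = 25 points per surplus kit

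| Case | K | I | SAP formula | Injection-based |
|---|---|---|---|---|
| Four kits, four injections | 4 | 4 | 4/4 = 100% | 4/4 = 100% |
| Three kits, three injections | 3 | 3 | 3/4 = 75% | 3/4 = 75% |
| Four kits, one not injected | 4 | 3 | 4/4 = 100% | 3/4 = 75% |
| Four kits, two not injected | 4 | 2 | 4/4 = 100% | 2/4 = 50% |
| Four injections, one replacement kit | 5 | 4 | 5/4 = 125% | 4/4 = 100% |

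The formula is right when every kit is injected, and it also handles a visit at which no kit was allocated. It is wrong in the last three rows, and in each of them the participant changes category.

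**Against exposure (SAP 3.4.1: last dose date − first dose date + 1)**
- Day 57 kit recorded but not injected: exposure is 29 − 1 + 1 = 29 days, beside 100% compliance. The listing contradicts itself.
- Day 29 kit recorded but not injected, Day 57 given: exposure is 57 − 1 + 1 = 57 days, beside 100% compliance. Neither figure shows the missed dose.

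**Against sensitivity analysis 1 (SAP 4.1.3).** That analysis requires receipt of all four doses. Both participants above would be excluded from it while shown as fully compliant.

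**The end of the study in the denominator.** Protocol 4.4 defines the end of the study as the last participant's last visit. SAP 3.1.1.3 and 3.1.1.5 use an end-of-study date beside the date of death, which reads as the participant's own. For someone who withdraws after two doses and before Day 29:
- participant level: 2/2 = 100%
- trial level: 2/4 = 50%

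Someone who stops treatment after two doses but attends the follow-up in protocol 7.1 scores 2/4 = 50% on either reading.

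**The case against.** The case for leaving the formula alone is fair in several respects. Protocol 6.4 has study drug given directly by the investigator, a designee or site staff, and at the site a second person confirms dose and identity. There is no take-home supply, so a kit allocated but not injected should be rare. The documents do not say that the kit is assigned before results are reviewed, nor how a replacement vial is logged. The likelier kind of missed dose, a visit not attended, is already counted because the denominator includes visits not done. Percent compliance enters no model; sensitivity analyses 1 and 2 work from doses actually received, and IP deviations are an important-deviation category of their own. SAP 4.2.8.2 asks only for a continuous summary, so a change of category may never be tabulated. All of this stands. It limits the size of the problem but does not make a kit record evidence of an injection.

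A reader might go further and infer that an arm needing several kits per dose would show inflated compliance, so that arms would differ only by vial count. The documents do not support this. Strengths and doses are redacted, and that cannot be held against the plan. The visible text points to one kit per visit: a single kit number at the dispensing visit, "Each vial will be packed in a separate carton" (protocol Table 4), and a SAP denominator that equates vials with visits. Protocol 6.1.1 does say that "the investigational product strength/concentrations may be used for other cohorts than presented in" the table, but the stated purpose is to keep injection volume small, and it says nothing about multiple kits.

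Nor does a participant-level denominator amount to an error. Compliance while in the study is a legitimate quantity; what is missing is a statement of which one is meant.

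**Conclusion.** The concern holds as a limited defect in a descriptive measure. As written, an uninjected or replacement kit counts as a dose taken and moves that participant's compliance by 25 points: 75% to 100%, or 100% to 125%. This assumes one kit per dose, four scheduled visits, and that the IRT logs allocation only, as protocol 6.3 describes. The frequency cannot be derived from the documents and should be low.

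The effect is confined to the compliance table and listing. These can disagree with exposure and with sensitivity analysis 1; it would be too strong to say that they will. The primary analysis is untouched. The change is still worth making, because the better record is already collected and already used for exposure.

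**What to change.** In SAP 3.4.2:
1. Take the numerator from injections recorded as administered in the eCRF treatment log, and the denominator from scheduled doses.
2. State whether the end of the study in the denominator is the participant's or the trial's.
3. Add a table of the number of doses received (1, 2, 3, 4) by arm. It shows early withdrawals plainly under either denominator.
4. Keep IRT kit counts for accountability listings only.

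Before relying on the log, reconcile protocol 6.4, which for home doses mentions only source documents, with SAP 3.4, which sends clinic and home doses alike to the eCRF.

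The cost is a paragraph of SAP text, minor reprogramming and one small table. Reported compliance may fall slightly.

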### **3.5 Concomitant medications and procedures**

Subjects can undergo concomitant medications or procedure deemed necessary to provide adequate supportive care except for those medications identified as restricted and prohibited as listed in the study protocol and detailed (coding and indication wherever applicable) in the in the IDRP.

The eCRF collects concomitant medications and procedures. The WHO-DD March 2019 B3 Global or higher is used to classify medications. MedDRA version 23.0 or higher is used to classify procedures.

Medications and procedures are classified as concomitant as below:

The imputation method described in section 3.1.1.5 is used in case the medication / procedure end date is partially missing. The imputation method described in section 3.1.1.1 is used in case the first dose of IP date and time are missing or partially missing.

After the end date imputation, the medications and the procedures will be classified as either prior or concomitant (but not both) according to the end date. Prior medication or procedure is defined as any medication / procedure with an end date prior to the first dose of study drug (exclusive). Concomitant medication / procedure is defined as any medication / procedure with an end date on or after the first dose of study drug, or any medication / procedure that is ongoing at the end of the study. Medications and procedures with completely missing end date are classified as concomitant.

Prohibited concomitant medications are confirmed and flagged by the study physician in accordance with the study protocol.

## **4 ANALYSIS METHODS**

All analyses method described in this section will be applicable to both the analyses, primary and final.

## 4.1 General principles

Unless otherwise specified, for continuous variables, descriptive statistics will include the number of subjects (n), mean, SD, median, minimum and maximum. For log-normal variables also the Geometric mean and Geometric CV will be used.

For categorical variables the number and percentages of subjects by categories will be tabulated. Percentages will be calculated based on the number of subjects with no missing data, i.e., will add up to 100%. Categories with count of zero will be not displayed.

Unscheduled analysis visits will not be used in descriptive statistics. Unscheduled analysis visits will only be reported in listings and used where explicitly needed.

For continuous variables, descriptive statistics will be summarized for the observed values, and where specified, also for changes from baseline and relative or percent change from baseline.

Changes from baseline, in certain categorical variables will be summarized using shift tables. The number and percent of subjects within each treatment group will be generated for each category post-baseline by baseline category.

If not otherwise specified, all the analyses will include the post IP-discontinuation data for those subjects who discontinue from study treatments but are still followed up for their scheduled visits.

The following statistical models will be used:

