### 4.2 Scientific Rationale for Study Design

AstraZeneca is developing AZD8233 for the treatment of dyslipidemia. This study aims to

evaluate the effect of different doses of AZD8233 on LDL-C at steady state to select a therapeutic dose for further clinical development.

The scheduled 12 weeks dosing should be sufficient to reach close to steady state conditions in the tissues at the end of the dosing period (estimated terminal half-life of the full length ASO in plasma is 2-3 weeks). Based on these data and the expected time course for PCSK9 and LDL-C reduction, 12 weeks of dosing is predicted to allow for a robust assessment of safety, tolerability, PK, as well as PCSK9 and LDL-C reduction to guide dose selection for further clinical development of AZD8233.

Dosing and follow up schedule were selected based on the long estimated terminal half-life of the full length AZD8233 ASO in plasma as well as the observed time course for PCSK9 levels to return to baseline after single dose administration in man. Monthly dosing is predicted to result in a low level of fluctuation of PCSK9 levels and tissue exposure during dose intervals.

Dosing in the current study will only start after AZD8233 is concluded safe and tolerable by the Safety Review Committee in Study D7990C00002. The definition of safe and tolerable is that none of the pre-specified safety stopping criteria in Study D7990C00002 have been met.

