**Table 2 Populations for Analysis**

Population/Analysis set	Description
All enrolled subjects	All participants who sign the ICF.
All randomized subjects	All participants who were randomized. Participants will be analysed according to the treatment to which they were randomized.
Full analysis set	All randomized participants who received at least one dose of IP, in accordance with the intention to treat principle. Participants will be included in the analysis according to the treatment to which they were randomized. This is the primary analysis set.
Safety analysis set	All participants randomly assigned to study treatment and who take at least 1 dose of study treatment and for whom any post-dose data are available. Participants will be analysed according to the treatment which they actually received. If a participant received study intervention from the wrong kit for only part of the treatment duration and then switched to another, the associated treatment group for that participant will be the treatment group that participant was randomized to.
ADA analysis set	All participants randomly assigned to study treatment and who take at least 1 dose of study treatment and had at least one ADA assessment available. Participants will be included in the analysis according to the treatment to which they were randomized.
PK analysis set	All participants in the full analysis set who have at least one PK sample post dose. A patient will be considered as having at least one PK sample post dose if he has at least one plasma concentration that is not below LLOQ after the first dose. Subjects will be analysed according to the treatment which they actually received. However, only samples taken on patients planned to receive active

	treatment are analysed. Thus, patients planned to receive placebo but who finally received active treatment will not have any result available.
--	---

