### **3.3.2.5 Pharmacokinetic parameters**

PK concentrations are tested in a central external laboratory as per scheduled timepoints.

PK concentrations are assigned to the analysis visits as described in section 3.1.2. Measurements with missing or partial missing dates are not assigned to any analysis visit. PK concentrations below the LLOQ for which the exact value cannot be determined, will be replaced with the LLOQ.

PK parameters are not derived and analysed within this SAP. Details on pharmacokinetic parameters are provided in an additional bioanalytical report prepared by a dedicated pharmacometrics support group at AstraZeneca.

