#### **4.2.5.3 Pharmacokinetic parameters**

The analysis will be based on the PK analysis set.

Plasma concentrations will be summarized descriptively as a continuous log-normal variable at each analysis visit and scheduled time. The geometric mean +/- the geometric standard deviation will be also reported together with the number of samples below the limit of quantification. The geometric mean +/- the geometric standard deviation is calculated as the  $\exp(\text{mean}(\text{variable in log}) \pm \text{SD}(\text{variable in log}))$ . Plasma concentrations will also be listed for all subjects in the PK analysis set. Listings of all subjects excluded from the PK analysis set will also be provided. The listing will be based on all enrolled subjects.

PK parameters are not derived and analysed within this SAP. Derivations and results of the pharmacokinetic analyses are provided in an additional bioanalytical report prepared by a dedicated pharmacometrics support group at AstraZeneca.

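### By-visit plasma concentration summaries up to Day 85 would include samples from any participant who stopped dosing early, because the SAP makes no PK exception to its post-discontinuation rule

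*SAP*

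**What the plan says.** The default is in SAP 4.1. Unless another rule is given, "all the analyses will include the post IP-discontinuation data for those subjects who discontinue from study treatments" but are still followed at their scheduled visits. It gives way only where another section says otherwise.

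The PK text does not say otherwise:

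- SAP 4.2.5.3: "Plasma concentrations will be summarized descriptively as a continuous log-normal variable at each analysis visit and scheduled time". No dosing condition is attached.
- PK analysis set (SAP Table 2): "All participants in the full analysis set who have at least one PK sample post dose". One concentration not below the LLOQ after the first dose is enough, and no later sample is removed. On grouping: "Subjects will be analysed according to the treatment which they actually received". Stopping early does not move a participant to another group.
- SAP 3.3.2.5: "PK concentrations are assigned to the analysis visits as described in section 3.1.2", that is, by day window only.
- SAP 3.1.3 does not list PK among the data allocated to study phases, and its on-treatment phase in any case runs to the end of the study. No phase label would separate these samples.

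Such samples can arise. Protocol 7.1 and SAP 1.2 ask participants who stop treatment to attend an early discontinuation visit and then their scheduled visits, for three months in total. PK is drawn at the early discontinuation visit and on Days 8, 29, 43, 57, 71, 85, 113 and 141, pre-dose on the dosing days among them (Protocol Table 1, footnote i).

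**The concern.** Keeping data after discontinuation suits the LDL-C analysis, which compares arms as randomised whatever dosing followed. A concentration table answers a different question. A reader will take the Day 85 geometric mean for a dose as the level that the four-dose regimen produces four weeks after its last dose. A Day 85 sample from someone who never received the Day 57 dose is not such a level, yet under the rule as written it sits in the same cell.

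At stake are the by-visit geometric means and geometric CVs for each dose, and the boxplots of PK concentration by ADA status in SAP 4.2.5.4. If early stopping differed between arms, the apparent relation of concentration to dose would shift with it.

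**Working it through.** **The plan's own figures.** The documents give no figure on this point. Their one design figure, 20 per arm for 90% power (difference 0.33, SD 0.3), reproduces: a t-test needs 19 per arm, and 20 give 92.4%. The point does not rest on it.

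**Inputs from the documents**
- Doses on Days 1, 8, 29 and 57 (Protocol 4.1).
- Half-life: "estimated terminal half-life of the full length ASO in plasma is 2-3 weeks" (Protocol 4.2), so h = 14 or 21 days.
- 108 randomised 1:1:1:1 (Protocol 9.2), so 108/4 = 27 per arm. The 20 per arm is the evaluable target, not the number dosed.

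**Assumptions not in the documents:** equal doses; mono-exponential decay from each dose; all 27 sampled; 1, 2 or 4 participants per arm who stop and keep giving samples.

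**Step 1. Day 85 level.** Each dose on day d contributes 2^(−(85−d)/h).

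| Dose day | Days to Day 85 | h = 14 | h = 21 |
|---|---|---|---|
| 1 | 84 | 0.0156 | 0.0625 |
| 8 | 77 | 0.0221 | 0.0787 |
| 29 | 56 | 0.0625 | 0.1575 |
| 57 | 28 | 0.2500 | 0.3969 |
| All four | | 0.3502 | 0.6956 |

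**Step 2. Ratio r of a participant who stopped to a completer**
- Last dose Day 8: 0.0377/0.3502 = 0.108; 0.1412/0.6956 = 0.203.
- Last dose Day 29: 0.1002/0.3502 = 0.286; 0.2987/0.6956 = 0.429.

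**Step 3. Arm geometric mean.** With n such participants among 27, it is multiplied by r^(n/27). For n = 2:
- Last dose Day 8: 0.108^(2/27) = 0.848; 0.203^(2/27) = 0.889. A fall of 11% to 15%.
- Last dose Day 29: 0.286^(2/27) = 0.911; 0.429^(2/27) = 0.939. A fall of 6% to 9%.

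Range over the assumed n:

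| n of 27 | Fall, last dose Day 8 | Fall, last dose Day 29 |
|---|---|---|
| 0 | 0 | 0 |
| 1 | 6% to 8% | 3% to 5% |
| 2 | 11% to 15% | 6% to 9% |
| 4 | 21% to 28% | 12% to 17% |

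**Step 4. Which visits are affected**
- Day 8: none, since only the Day 1 dose precedes the sample.
- Day 29 (pre-dose): only if the Day 8 dose was missed.
- Days 43 and 57 (Day 57 is pre-dose): only if the Day 29 or an earlier dose was missed. With last dose Day 8, r at Day 43 is 0.3018/0.8018 = 0.376 (h = 14) or 0.5650/1.1949 = 0.473 (h = 21), and the same at Day 57. Two of 27 then lower the geometric mean by 5% to 7%.
- Days 71 and 85: any missed dose matters. The ratios in Step 2 apply to both days, since no dose falls between them.
- Day 113 onward: everyone is washing out, so mixing shifts the level only.

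**Step 5. What works the other way.** SAP 3.3.2.5: "PK concentrations below the LLOQ for which the exact value cannot be determined, will be replaced with the LLOQ". This can only raise a low value, so it shrinks the falls above where it applies. The documents do not give the LLOQ, so the amount is unknown.

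**The case against.** The strongest reply is that nothing formal depends on this table. The secondary PK endpoint is population PK parameters in a separate report, and the SAP derives no PK parameters. Protocol 9.4.2.2 asks only for descriptive statistics at each sampling time, which the SAP delivers. The documents do not call the table an estimate of on-regimen exposure and give no number of participants expected to stop. This stands as a limit on scope. It does not supply the missing rule: the default, followed as written, puts under-dosed samples into cells labelled by dose.

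A reader might infer more than the documents support:

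- **That every analysis includes these data.** The rule is a default. Sensitivity analysis 1 (SAP 4.1.3) is an exception, restricted to participants who received all four doses.
- **That exposure will be understated.** The effect is zero unless someone stops before Day 57 and keeps giving samples.
- **That Day 43 to Day 169 are all contaminated.** After an on-schedule Day 29 dose, the Day 43 and pre-dose Day 57 samples are valid levels of the regimen. The three-month limit may also end sampling before Day 169.
- **That dose selection is distorted.** Protocol 4.2 names PK among the assessments meant to guide it, but the study rationale and Protocol 4.3 tie it to LDL-C and PCSK9 reduction, and no passage assigns the by-visit table that use.
- **That the SAP contradicts the protocol's requirement of evaluable PK data.** Neither document defines that term for single samples, so no contradiction is shown.

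**Conclusion.** The point holds for the SAP's descriptive PK outputs: the by-visit concentration summaries from Day 29 to Day 85, and the ADA-by-PK boxplots. The direction is downward relative to participants dosed on schedule. On the stated assumptions, two of 27 participants stopping after Day 8 or after Day 29 would lower an arm's Day 85 geometric mean by about 11% to 15% or 6% to 9%, less any LLOQ effect. The half-life and dosing days come from the protocol. Equal doses, exponential decay and the number stopping are assumptions.

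The population PK model is not shown to be affected, because its handling of dosing history is left to a separate plan. The LDL-C and PCSK9 analyses are not affected. The change is still worth making, because it is cheap and settles in advance which concentrations count.

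**What to change.** Add to SAP 4.2.5.3: by-visit descriptive statistics of plasma concentration, and the PK boxplots in SAP 4.2.5.4, exclude samples for which any dose scheduled before that sample was missed or not given as randomised; these samples are flagged and kept in the listing. A summary of all samples may be shown alongside.

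Two details matter:

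- The condition covers every earlier scheduled dose, not only the latest. Otherwise a Day 43 sample from someone who missed Day 8 but received Day 29 would stay in.
- It depends on doses, not on the date of discontinuation. Samples taken after the decision to stop stay in if all prior scheduled doses were given. Pre-dose samples on Days 8, 29 and 57 are judged on earlier dosing days only.

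Sensitivity analysis 2 (SAP 4.1.4) already separates visits by whether the previous scheduled dose was given as planned, so the flag extends existing logic. Leave the LDL-C and PCSK9 analyses unchanged.

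Cost: one sentence and one flag derived from the dosing log. The table has slightly fewer samples per visit, and the PK boxplots may rest on slightly fewer samples than the companion PCSK9 and LDL boxplots.
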